Once the plexus has been identified, the needle is passed through the skin, platysma, and investing layer of the deep cervical fascia, and the tip is placed adjacent to the plexus. . Following negative aspiration, 1–2 mL of normal saline is injected to confirm the proper injection site. Then after confirmation of safe needle position and absence of vascular spread, bupivacaine 0.25% (5–15 mL) is administered to envelop the plexus, and the block is repeated with the same technique on the opposite side.

(Figure 1).

[figure not shown]

Figure 1. *Cervical plexus (transverse view): desired distribution of local anesthetic (blue-shaded area) to nerve block the cervical plexus. Needle path: 1. ASM, anterior scalene muscle; CA, carotid artery; CP, cervical plexus; MSM, middle scalene muscle; SCM, sternocleidomastoid muscle.*

Group B: *Induction of general anesthesia as Group A, without performing intermediate cervical plexus block, intravenous morphine will be given in a dose of 0.1-0.2mg/kg to maintain intraoperative analgesia.*

All operations will be performed in the morning, taking into consideration circadian rhythm of hormone release. In both groups, venous blood samples to measure serum cortisol and interleukin-6 level will be collected before surgery as a baseline, then 24 hours post-operative. interleukin-6 is normally low and may be undetectable within 30-60 min after start of surgery while reaching maximum level at 24 hours post-operative.

During the intraoperative period; heart rate and mean arterial blood pressure will be recorded every 15 minutes throughout the surgery. Intravenous fentanyl bolus doses (0.5 µg/kg) will be adjusted to keep the HR and mean arterial blood pressure within 20% of the pre-induction values.

At the end of surgery, atracurium will be stopped and neuromuscular blockade will be reversed with intravenous neostigmine 0.04 mg/kg and 0.01 mg/kg atropine and endotracheal tube will be removed.

After operation, patients will be transferred to post anesthesia care unit (PACU) for complete recovery and monitoring. A standard postoperative analgesia regimen will be prescribed as intravenous paracetamol 1gm every 8 hours. Intravenous morphine 0.05 mg/kg will be given as a rescue analgesic dose if numeric analogue score was ≥ 3 . Metoclopramide 0.15 mg/kg IV will be prescribed for patients complaining of nausea or vomiting.

The maximum dose of morphine that will be given is 20 mg/24 hrs.

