The block will be considered a failed block if the patient required more than two doses of rescue analgesia in the first hour postoperatively.

Measurement tools

- *Demographic data: age, sex, body mass index (BMI).*
- *Serum cortisol and interlukien-6 pre-operative and 24 hours post-operative.*
- *Hemodynamics {heart rate, arterial blood pressure (systolic, diastolic and mean blood pressure)} will be recorded at the following intervals: baseline reading , Intraoperative 15 minutes post-intubation (pre-block), 15 minutes after the block/administration of morphine and then every 15 minutes throughout the surgery, and postoperative at 1,6,12, 24 hours..*
- *NPRS score at 15, 30, and 60 min, 6, 12, 24 hours post-operatively.*
- *Number of patients in each group who need intraoperative additional analgesic doses of fentanyl and total fentanyl dose for each patient.*
- *Total postoperative analgesic requirements.*
- *Failure rate of the block (the block will be considered a failed block if the patient required more than two doses of rescue analgesia in the first hour postoperatively).*

VI. Study outcomes

1. Primary outcomes:

- *The serum cortisol level 24 hours postoperatively.*

2. Secondary outcomes:

- *The serum interleukin-6 24 hours postoperatively.*
- *Intraoperative hemodynamics {heart rate, arterial blood pressure (systolic, diastolic and mean blood pressure)}*
- *Intraoperative additional fentanyl requirements.*
- *NPRS score postoperative during 1st 24 hours. 15, 30, and 60 min, 6, 12, and 24 hours after surgery.*
- *Time to first postoperative analgesic request (duration of analgesia).*
- *Block failure rate.*
- *Incidence of complications. (Nerve injury, Hematoma formation, LA toxicity, intravascular injection.*
- *Block failure: The block will be considered a failed block if the patient required more than two doses of rescue analgesia in the first hour postoperatively.*

Statistical Analysis

Statistical Analysis

I. Sample size

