Our primary outcome is the serum cortisol level 24 hours postoperatively. In a previous study, the serum cortisol level after 24 hours was 21.8 ± 4.7 micrograms per deciliter (mcg (ref) after lumbar fixation surgeries. We calculated a sample size that could detect a mean difference of 20% between both study groups. MedCalc Software version 14 (MedCalc Software bvba, Ostend, Belgium) was used to calculate the sample size 60 patients (30 Patient per group) at least were estimated to have a study power of 95% and an alpha error of 0.05. This number will be increased to 66 patients (33 patients per group) to compensate for possible dropouts.

Sample size calculation was performed guided by power of 95%, confidence level of 95 %.(8)

II. Statistical analysis

For data analysis, the Statistical Package for Social Science (SPSS) software, version 26 for Microsoft Windows (SPSS Inc., Chicago, IL, USA) will be used. The Chi squared test will be used to examine categorical data, which will be given as frequency (percent). The Shapiro-Wilk test will be used to verify for normality in continuous data, and the results will be provided as mean (standard deviation) or median (interquartile range) as appropriate. Depending on the data's normality, the unpaired t test or the Mann Whitney test will be used to assess it. Repeated measures will be examined using analysis of variance (ANOVA), with post-hoc pairwise comparisons using the Bonferroni tests. A P value less than 0.05 will be considered statistically significant.

References

References:

1. Arfanis K, Fioratou E and Smith A: Safety culture in anaesthesiology: Basic concepts and practical application. *Best Pract Res Clin Anaesthesiol* 25: 229-238, 2011.

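### Rescue morphine is triggered by the same pain score that is compared between groups, and the analysis takes no account of it, so NPRS differences after the first score may be understated

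*Combined protocol and SAP*

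**What the plan says.** - **Outcome.** Study outcomes, secondary list: "NPRS score postoperative during 1st 24 hours. 15, 30, and 60 min, 6, 12, and 24 hours after surgery". That is six scores per patient.
- **Rescue.** Study Procedures, Study Protocol: "Intravenous morphine 0.05 mg/kg will be given as a rescue analgesic dose if numeric analogue score was ≥ 3". No group is exempted. I take the score named there to be the NPRS, the only numeric pain scale the protocol defines. There is a ceiling: "The maximum dose of morphine that will be given is 20 mg/24 hrs".
- **Background treatment.** "A standard postoperative analgesia regimen will be prescribed as intravenous paracetamol 1gm every 8 hours", with no distinction by group. Group B alone also has an intraoperative opioid: "intravenous morphine will be given in a dose of 0.1-0.2mg/kg to maintain intraoperative analgesia".
- **Repeat rescue is foreseen.** "The block will be considered a failed block if the patient required more than two doses of rescue analgesia in the first hour postoperatively".
- **Analysis.** For continuous data: "Depending on the data's normality, the unpaired t test or the Mann Whitney test will be used to assess it". Repeated measures go to ANOVA with Bonferroni comparisons. The section does not say which of these applies to NPRS, and it does not mention rescue.
- **Companion measures.** Time to the first analgesic request is a secondary outcome. Total analgesic use after surgery appears under Measurement tools but not under Study outcomes.

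**The concern.** A patient who scores 3 or more becomes eligible for morphine, and in the first hour the next scheduled score follows 15 or 30 minutes later. That later score reflects morphine as well as the allocated treatment. A Group B patient made comfortable by several rescue doses then counts the same as a Group A patient who is comfortable with none. If the block reduces pain, Group B should reach the threshold more often and receive more morphine, so the later NPRS difference understates the block's effect.

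At stake is the second half of the hypothesis, which claims adequate analgesia after surgery, and the objective on pain over the first 24 hours. The error would run toward missing a benefit, not toward inventing one.

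**Working it through.** **1. The plan's own figures.** The documents give no mean, SD or target difference for NPRS, so there is no NPRS figure to reproduce. The only sample size is for 24-h cortisol: 2 × (1.96 + 1.645)² × (4.7 / 4.36)² = 30.2 per group, where 4.36 = 20% of 21.8. The plan states 30 per group, which gives 94.9% power by the normal approximation. That agrees closely and does not depend on NPRS.

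**2. Which scores are exposed.**
- 15 min: largely before any rescue.
- 30 and 60 min: 15 and 30 minutes after the preceding score, inside the hour in which the block-failure definition foresees more than two doses.
- 6, 12 and 24 h: 5, 6 and 12 hours after the preceding score. The documents give no duration for a rescue dose, so carry-over here is less clear.

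**3. Direction and size.** Let D be the difference (B minus A) in a score without rescue, p_A and p_B the proportions rescued at the score before, and e the points by which rescue lowers the next score. Ignoring the floor at 0,

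observed difference ≈ D − e × (p_B − p_A).

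The difference shrinks only if p_B exceeds p_A.

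**4. Illustration.** Every NPRS input is an assumption: Group B mean 3 to 5, block effect 1 to 2 points, SD 1.5, within-patient correlation 0.7, and rescue lowering the next score by 0.5 to 2 points. Scores are rounded and limited to 0–10. Each scenario had 600 simulated trials of 30 per group, tested by Mann-Whitney, so power carries a simulation error of about 2 percentage points (√(0.5 × 0.5 / 600) = 0.020).

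| B mean | Block effect | e | Rescued A / B | Difference without → with rescue | Shrinkage | Power without → with |
|---|---|---|---|---|---|---|
| 5 | 1 | 0.5 | 84% / 95% | 1.00 → 0.94 | 6% | 69% → 65% |
| 3 | 2 | 0.5 | 16% / 63% | 1.80 → 1.56 | 13% | 100% → 99% |
| 4 | 1.5 | 1 | 50% / 84% | 1.45 → 1.11 | 23% | 95% → 88% |
| 3 | 1 | 1 | 37% / 63% | 0.92 → 0.66 | 28% | 66% → 49% |
| 4 | 1.5 | 2 | 50% / 84% | 1.48 → 0.76 | 49% | 97% → 59% |
| 3 | 1 | 2 | 37% / 63% | 0.94 → 0.41 | 56% | 66% → 26% |

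The formula agrees. For the last row, 0.94 − 2 × (0.63 − 0.37) = 0.42, against 0.41 simulated. A slightly different model (means 4.0 and 2.5, between-patient SD 1.2, occasion SD 0.9) gives 1.47 without rescue, 1.12 with a 1-point effect and 0.76 with a 2-point effect. Power is then about 95%, 87% and 59%.

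The 6% and 56% rows are the extremes of all scenarios run. Group B was rescued more often in every one, because each assumed that the block reduces pain and none modelled Group B's intraoperative morphine.

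**The case against.** - **Comparing pain regardless of rescue is a legitimate treatment-policy comparison.** This stands, provided it is declared and read beside rescue use. The plan does neither. It also never says that post-rescue scores are to be regarded as unaffected; that would be an inference from silence.
- **Other measures reveal the block's effect.** A reader might infer that a null NPRS result could not be told apart from successful rescue. The documents do not support that. The 15-min score is largely before rescue, later rescue does not alter time to first request, and total analgesic use is recorded in both groups. In the 4.0 versus 2.5 illustration, the first score alone was significant in about 96% of simulated trials and the rescue proportions (84% versus 50%) in about 82%. The protection is partial: these measures do not correct the NPRS comparison, and analgesic use has no outcome status.
- **The direction is not certain.** This stands for the early scores. Group B's intraoperative morphine could lower its early pain and narrow or reverse the rescue imbalance. The ceiling on morphine also means that not every qualifying score must bring a dose.
- **The size is assumption-only and models one pair of scores.** This stands. It fits the first hour and should not be carried over to 6, 12 and 24 h.
- **A joint score is no cleaner.** Partly right. It has no natural unit, and rescue morphine after surgery leaves out Group B's intraoperative dose, so it does not isolate the block. That argues for a supportive role, not for replacing NPRS or making it merely descriptive.

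**Conclusion.** The gap is real but limited. If Group B is rescued more often, planned NPRS comparisons after the first score understate the block's effect, most clearly at 30 and 60 min. The documents do not fix the amount: shrinkage ran from about 6% to 56% under the assumptions shown, with almost no loss of power when the block effect was 2 points and the rescue effect 0.5. A reader might infer that the difference is roughly halved; that holds only near the largest assumed rescue effect. The point concerns one secondary outcome, biases toward no difference, and leaves the 24-h cortisol analysis and its sample size untouched. The change is a cheap improvement worth making before data are seen.

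**What to change.** 1. Keep the planned NPRS comparison at each time, and state that it compares scores regardless of rescue.
2. List 24-h postoperative rescue morphine (mg/kg) as a secondary outcome, reported beside NPRS.
3. Pre-specify one supportive joint comparison. Rank all analysed patients, both groups together, on NPRS over 24 h and again on 24-h rescue morphine; add the two ranks; compare groups by Mann-Whitney, already in the plan. Choose the mean or the area under the curve in advance. From 0.25 to 24 h, the stretch after 1 h makes up 23 / 23.75 = 97% of the area's time span, so the area gives the first-hour scores little weight; a simple mean weights all six scores equally.
4. Record each NPRS before any rescue dose at that time point, and note the time of every dose.

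In simulation under assumed inputs, a joint comparison of this kind kept about 82% to 99% power where single post-rescue scores fell to 24% to 59%. Part of that gain comes from counting the rescue difference itself, so it answers a broader question than pain score alone.

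The cost is a few lines in the analysis section and dose times on the drug chart; both components are already collected. The downside is that the joint score has no natural unit, so both components must be shown with it. No change to the rescue rule is implied.

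### Time to first analgesic request has no rule for patients who never make a request; dropping them could bias the comparison in either direction

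*Combined protocol and SAP*

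**What the plan says.** Section VI (Study outcomes) lists "Time to first postoperative analgesic request (duration of analgesia") among the secondary outcomes. No start time, event definition or observation window is given for it. A 24 h horizon can only be inferred from neighbouring items such as "NPRS score postoperative during 1st 24 hours. 15, 30, and 60 min, 6, 12, and 24 hours after surgery".

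Section II of the Statistical Analysis names chi-squared for categorical data, repeated-measures ANOVA, and for continuous data: "Depending on the data's normality, the unpaired t test or the Mann Whitney test will be used to assess it". It contains no time-to-event method, no censoring rule, no value for a patient without an event, and no missing-data rule.

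The Study Protocol part of section V describes the analgesia that determines the event:
- Scheduled, for everyone: "A standard postoperative analgesia regimen will be prescribed as intravenous paracetamol 1gm every 8 hours".
- Rescue, triggered by a score: "Intravenous morphine 0.05 mg/kg will be given as a rescue analgesic dose if numeric analogue score was ≥ 3".
- Control arm, during surgery: "intravenous morphine will be given in a dose of 0.1-0.2mg/kg to maintain intraoperative analgesia".

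The Measurement tools list includes "Total postoperative analgesic requirements" but not the time of the first request.

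**The concern.** A patient whose pain score stays below the rescue threshold can reach the end of observation with no event, and so with no time to enter. In the block arm this could happen because the block works. In the control arm it could happen because of intraoperative morphine. Scheduled paracetamol makes it plausible in both. A t test or Mann-Whitney run on the recorded times would leave these patients out unless someone decides otherwise.

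Leaving them out conditions on something that happens after randomisation and that treatment may influence. The patients who remain are no longer randomised groups, and those with the best analgesia are the ones removed. The reported duration of analgesia, and the difference between arms, would then depend on a handling choice that the plan leaves open until the data are in.

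The event is also unclear. The outcome speaks of a request, whereas the procedures describe rescue triggered by a score. Nothing says that scheduled paracetamol does not count.

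**Working it through.** **The plan's own figure.** The documents give no figure for this outcome. Their only calculation is for cortisol: 2 × (4.7 × (1.960 + 1.645) / 4.36)² = 30.2 per group, where 4.36 is 20% of 21.8. That agrees closely with the stated 30 and has no bearing on this point. It supplies only the 30 per arm used below.

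**Assumed inputs.** Request times and non-request shares are assumptions. Observation ends at 24 h (inferred), and tests are two-sided at 0.05. *Kept* counts a patient without a request at 24 h; *dropped* removes that patient.

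**Case 1: exponential times, medians 18 h (block) and 8 h (control).** With λ = ln 2 / median and p = exp(−24λ) = share with no request by 24 h:
- Kept mean = (1 − p)/λ. Dropped mean = 1/λ − 24p/(1 − p).
- Block: λ = 0.0385, p = 0.397. Kept 15.66 h; dropped 25.97 − 15.79 = 10.18 h.
- Control: λ = 0.0866, p = 0.125. Kept 10.10 h; dropped 11.54 − 3.43 = 8.11 h.
- Difference: **5.6 h kept, 2.1 h dropped**. A simulation of 800 trials gave about 5.4 h and 2.0 h.

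**Case 2: nearly everyone requests (exponential, medians 4 h and 2 h).** The same formulas give p = 0.016 and 0.0002, and a difference of 5.68 − 2.89 = 2.8 h kept and 5.39 − 2.88 = 2.5 h dropped.

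**Case 3: the block only raises the share who never request.** Take 30% against 5%, with the same times for requesters in both arms (mean 7.06 h, from an exponential of median 6 h cut off at 24 h). Kept: (0.30 − 0.05) × (24 − 7.06) = 4.2 h. Dropped: 0.

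**Cases 4 to 6: a share never requests; the rest have lognormal times, medians 8 h and 4 h, log-SD 0.5.** Among that remainder, the mean limited to 24 h is 8.99 h (block) and 4.53 h (control). Among those with an observed time it is 8.78 h and 4.53 h.
- 20% in each arm. Kept: (0.8 × 8.99 + 0.2 × 24) − (0.8 × 4.53 + 0.2 × 24) = **3.6 h**. Dropped: 8.78 − 4.53 = **4.3 h**. The 800-trial simulation gave about 3.7 h and 4.3 h.
- 10% block, 20% control. Kept: (0.9 × 8.99 + 2.4) − (0.8 × 4.53 + 4.8) = 2.1 h. Dropped: 4.3 h.
- 30% block, 20% control. Kept: (0.7 × 8.99 + 7.2) − (0.8 × 4.53 + 4.8) = 5.1 h. Dropped: 4.3 h.

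**Power by simulation** (MW = Mann-Whitney; 30 per arm, except case 3 with 33; 4,000 trials for cases 1 to 3, 1,200 for cases 4 to 6):

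| Case | Mean difference kept → dropped | MW, dropped | MW, kept with ties | Log-rank |
|---|---|---|---|---|
| 1. Exponential 18 vs 8 h | 5.6 → 2.1 h | 16% | 70% | 78% |
| 2. Exponential 4 vs 2 h | 2.8 → 2.5 h | 58% | 61% | 75% |
| 3. 30%/5%, same requester times | 4.2 → 0 h | 5% | 41% | 68% |
| 4. 20%/20%, lognormal 8 vs 4 h | 3.6 → 4.3 h | 99% | 84% | 49% |
| 5. 10%/20%, lognormal 8 vs 4 h | 2.1 → 4.3 h | 99% | 74% | 23% |
| 6. 30%/20%, lognormal 8 vs 4 h | 5.1 → 4.3 h | 99% | 93% | 70% |

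Repeat runs agree within about 4 points; for case 1 the 800-trial run gave 15%, 67% and 74%. With equal exponential or lognormal medians in both arms (8 h or 18 h), the type I error of all three analyses was 4.1 to 5.3%. Seeing events only at the scheduled pain scores changes case 1 little (15%, 70%, 75%).

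**The case against.** The strongest reply is that no harm is written into the plan. No sentence says patients without a request are excluded, and the planned Mann-Whitney is valid if they are kept and share the top rank. On this view the gap is an unstated data-handling rule, not a wrong test. That stands as far as it goes. The gap remains, because the plan does not state the rule and the t test branch has no equivalent remedy on observed times.

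A reader might infer that dropping these patients must shrink the difference and hide a benefit of the block. The documents do not support that. They give no request rates, and controls receive intraoperative morphine, so which arm would have more non-requesters is unknown. Cases 4 and 5 show the difference growing. Case 6 shows it shrinking with no loss of power. The 99% power in those cases does not favour dropping, because the test then compares groups selected after randomisation.

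A reader might also infer that log-rank is the one correct test. It leads in cases 1 to 3 and trails Mann-Whitney with ties in cases 4 to 6, so neither is uniformly better.

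Finally, this is one of several secondary outcomes, which is true and limits the weight of the point.

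**Conclusion.** The point holds in a conditional form. A time-to-event secondary outcome is paired with tests that have no value for a patient without an event, and the plan is silent on such patients. If they are dropped, the bias can go either way. The difference shrinks when clearly more block patients make no request (5.6 h to 2.1 h in case 1). It can grow when non-request shares are equal or higher in control (3.6 h to 4.3 h in case 4). If nearly everyone requests rescue, the effect is small (2.8 h to 2.5 h in case 2).

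These sizes rest on assumed request times and shares and on an inferred 24 h window. They show what could happen and do not forecast this trial. The cortisol analysis and the sample size are not affected. The change is still worth making, because it is cheap and an event time that was not recorded may not be recoverable later.

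**What to change.** State in the plan that every randomised patient is kept in this analysis, and add:

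- **Definitions.** Time zero (for example the end of surgery, which anchors the pain-score times); the event (either first request or first rescue dose, with scheduled paracetamol not counted); and the observation window (24 h, matching the pain-score schedule).
- **Recording.** Add the time of that event to the Measurement tools list.
- **One method, named in advance.** Either Kaplan-Meier with log-rank, censoring at 24 h or at last observation if earlier; or Mann-Whitney with all non-requesters tied at the top rank, provided everyone is followed to 24 h. Do not apply the t test to observed times only.
- **Reporting.** The proportion without a request at 24 h in each arm, and medians with 95% confidence intervals where reached. The proportion is needed because a median may not be reached: under exponential times with 30 patients, the block-arm median would not be reached in about 9% of trials if the true median were 18 h, and in 43% if it were 24 h.

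The cost is a few lines of wording and one recorded time per patient. Both methods are available in SPSS. The sample size, the primary analysis and all treatment rules stay as they are.

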This pattern, however, can be disrupted by any stressful situation, such as severe pain from surgery, which has been linked to a progressive rise in cortisol levels both intraoperatively and in the early postoperative period.

Cytokines are group of low molecular weight proteins that modulate the systemic inflammatory response elicited by surgical intervention. Increased levels of proinflammatory cytokines, including interleukin-6 (IL-6) which is the main cytokine responsible for inducing the systemic changes, is an early features of acute injury. Interleukin-6 could be a good marker for research purposes that reflects and compares postoperative stress levels.

Spine surgeries are increasingly being performed as short-stay surgical procedures, and anterior cervical decompression and fusion is one such procedure (3).Postoperative incisional pain has been described as moderate in intensity, requiring opioid analgesics in most cases. Nonetheless, opioid-related side effects such as nausea, vomiting, and respiratory depression are undesirable in these patients who are at risk for airway problems due to surgical retraction or wound hematoma(4).

Regional anesthesia inhibits the stress response to surgery and can also influence postoperative outcomes. . The endocrinal stress response to the surgical operation is reduced as a result of inhibiting afferent impulses from the surgical site. Furthermore, a reduction in this type of stress response is seen as a key indicator of a successful regional block.

Intermediate cervical plexus block (CPB) is a safe and simple technique that has been shown to provide good pain relief through blocking all four cutaneous branches of the

cervical plexus, as well as sensory and motor branches (5). Not only Intermediate (CPB) is superior to superficial CPB in terms of effectiveness, but also is safer than deep (CPB) (6).

There is a paucity of evidence for the effect of bilateral cervical plexus block for anterior cervical spine surgeries. Prior research had employed recovery questionnaire score, 24-h opioid usage and length of hospital stay in assessment of cervical plexus block effectiveness (7), however estimating the effect of Intermediate (CPB) on stress biomarkers as serum cortisol and interleukin-6 has not been discussed yet.

Aim of the work

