The aim of the present study is to investigate the effect of Bilateral Ultrasound-Guided intermediate cervical plexus Block combined with general anesthesia on the stress and inflammatory response in patients undergoing anterior cervical spine surgery (ACSS).

Objectives:

- *To compare between serum level of cortisol and interleukin-6 pre-operative and 24 hours post-operative in both groups.*
- *To identify Hemodynamics variables (mean arterial blood pressure and heart rate) peri-operatively.*
- *To assess the pain score during 1st 24 hours postoperative according to numeric pain rating scale (NPRS).*
- *To measure the incidence of complications within both groups.*

Hypothesis:

We hypothesize that intermediate cervical plexus block will offer a significant suppression of stress response and adequate post-operative analgesia in patients undergoing anterior cervical spine surgeries.

Ethical Considerations:

Our study will be conducted in Kasr El Aini Hospital, Cairo University after approval of the Research Ethics Committee. Full written informed consent will be obtained from the patients before inclusion in this study.

Methodology

Methodology

I. Study design:

A randomized controlled study.

II. Study setting and location:

The study will be conducted in the Neurosurgery operating rooms at Cairo University hospital.

III. Study population:

(66) Patients, aged from 18 to 65 years old, ASA physical status I-II, scheduled for anterior cervical spine surgery will be included in the study. Patients will be randomly allocated using concealed closed envelope method into one of two groups:

- Group A (n=33): will include the patients who will undergo bilateral ultrasound guided intermediate cervical plexus block after general anesthesia.*
- Group B (control group) (n=33): will include the patients who will undergo general anesthesia with conventional analgesia.*

IV. Eligibility Criteria

1. Inclusion criteria:

1. *ASA I & ASA II patients.*
2. *Age group: from 18 to 65 years old.*
3. *Patients undergoing anterior cervical discectomy or fixation.*
4. *Genders eligible for study: both sexes.*

2. Exclusion criteria:

- *Patient refusal.*
- *Patient Undergoing posterior fixation in addition to anterior.*
- *An allergy to local anaesthetics.*
- *Infection at block puncture site.*
- *Bleeding disorders (Coagulopathy: PTT > 40seconds, INR > 1.2, platelet count < 120 x 10³ / L.).*
- *Emergency surgeries & patients in sepsis.*

V. Study Procedures

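### The complications outcome has no respiratory, airway, voice or open adverse-event item, and two of its four events can hardly occur in the control arm, so it poorly serves the both-groups safety objective.

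*Combined protocol and SAP*

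**What the plan says.** The fourth item under Objectives is "To measure the incidence of complications within both groups". The matching secondary outcome under Study outcomes is "Incidence of complications. (Nerve injury, Hematoma formation, LA toxicity, intravascular injection". The four events are not marked as examples, and no general adverse-event item follows.

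The Measurement tools list has no complications entry, so no definition, assessor or assessment time is given. After surgery it covers heart rate and blood pressure (1, 6, 12 and 24 h), the pain score (15, 30 and 60 min, then 6, 12 and 24 h), analgesic requirements and block failure, plus the 24 h blood sample. Pulse oximetry is attached in the operating room (Study Protocol), but no saturation value is listed for recording.

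The background text before Aim of the work says the block acts on the cutaneous branches of the "cervical plexus, as well as sensory and motor branches". It calls opioid side effects, respiratory depression among them, "undesirable in these patients who are at risk for airway problems due to surgical retraction or wound hematoma". In the Group A procedure, "bupivacaine 0.25% (5–15 mL) is administered to envelop the plexus", and then "the block is repeated with the same technique on the opposite side". Group B receives intravenous morphine and no block.

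**The concern.** The plan raises respiratory and airway risk when it argues for the block, and then has no item for it among its outcomes in either arm. Group A receives local anaesthetic on both sides of the neck, and the plan itself says the block affects motor branches. Group B receives morphine, whose respiratory effect the plan calls undesirable in these patients. Respiratory events are therefore plausible in both arms and could favour either one.

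What is at stake is the safety statement at the end of the trial. If staff follow the list as written, a patient who desaturates, needs airway support or becomes hoarse after extubation has no prespecified place on the record form. A report of few or no complications could then reflect what was asked rather than what happened. The list also gives little information on Group B, although the objective covers both groups.

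**Working it through.** **1. The plan's own figure.** The plan calculates nothing for safety. Its one calculation is the cortisol sample size. The difference is 20% of 21.8 = 4.36, with SD 4.7, two-sided alpha 0.05 (sidedness assumed) and power 95%. Then n = 2 × (1.960 + 1.645)² × (4.7/4.36)² = 30.2, rounded up to 31 per arm, against the stated 30. This is close enough, and the point does not depend on it. It matters only because it fixes 33 per arm.

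**2. The four listed events, by arm.**

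| Listed event | Group A (block) | Group B (no block) |
|---|---|---|
| Nerve injury | possible | possible through surgery |
| Haematoma formation | possible | possible through surgery |
| Local anaesthetic toxicity | possible | hardly possible |
| Intravascular injection | possible | hardly possible |

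Only two of the four can inform both arms.

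**3. What the background raises, against what is recorded.**

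| Raised in the background | Outcome or measurement item |
|---|---|
| Airway problems (attributed to retraction or haematoma) | haematoma only; the airway event itself is not listed |
| Respiratory depression (attributed to opioids) | none |
| Nausea and vomiting (attributed to opioids) | none; only a treatment is described |
| Block of motor branches | none, unless undefined nerve injury is stretched to cover it |

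The block volume is 5 to 15 mL per side, so 10 to 30 mL over two sides.

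**4. Could such events occur in a trial of this size?** The documents give no rate, so the rates below are assumptions. Expected cases = 33p. Chance of at least one = 1 − (1 − p)^33.

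| Assumed rate p | Expected cases in 33 | Chance of at least one |
|---|---|---|
| 1% | 0.33 | 28% |
| 5% | 1.65 | 82% |
| 10% | 3.3 | 97% |
| 20% | 6.6 | over 99% |

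**5. What a zero would mean.** Even with systematic recording, 0 events in 33 has a two-sided 95% exact upper limit of 1 − 0.025^(1/33) = 10.6%.

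**6. Power for a between-arm comparison.** The figures sum over both binomial distributions with 33 per arm and two-sided 0.05. The rates are again assumed.

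| Rates compared | Uncorrected chi-squared | Fisher's exact |
|---|---|---|
| 10% vs 5% | 12% | 3% |
| 20% vs 10% | 21% | 12% |
| 20% vs 5% | 49% | 29% |

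So the added items can be described by arm but not usefully tested.

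**The case against.** The strongest reply is that the causal premise comes from outside the documents. They do not mention the diaphragm, phrenic nerve, vocal cords or Horner signs. Airway risk is attributed to surgery and respiratory depression to opioids; neither is attributed to the block. The needle target is described as superficial to the prevertebral fascia, and the background calls the intermediate block safer than the deep one. This stands: the link from the block to breathing or voice effects is a clinical inference. It does not remove the gap, because the plan itself names respiratory and airway events as relevant to these patients and records neither in either arm.

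A reader might infer that such events would be counted as zero whatever their true rate. The documents do not support that. The objective is worded without restriction, no word such as only limits the list, and nerve injury is undefined, so a phrenic or laryngeal deficit might be entered there. Ad hoc reporting is also possible. But nothing directs staff to look, and the text describes no blinding or sham block, so ad hoc reporting could differ by arm.

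A reader might also infer that adding the items would give a real between-group safety comparison. The power figures rule that out. Finally, the assumed rates have no anchor in the documents: they show what could happen, not how large the defect is.

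**Conclusion.** The point holds as a gap in safety recording. The list omits the respiratory and airway events that the plan itself raises and has no open adverse-event item. It rests half on events that can hardly occur in Group B, and it comes without definitions, times or assessor. Transient respiratory or voice effects may therefore be missed or recorded unsystematically. How many is unknown: the chance of at least one such case in Group A runs from 28% at an assumed 1% rate to over 99% at 20%.

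The conclusion rests on reading the list as the intended content of the outcome and on the clinical inference that a bilateral block can have such effects. It does not show that the block causes harm, or that a corrected list would detect a difference. The cortisol outcome, its sample size and its analysis are unaffected. This is a worthwhile, inexpensive improvement to one secondary outcome.

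**What to change.** Prespecify yes/no items for both arms:

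- oxygen desaturation below a threshold that the sponsor defines, or need for airway or ventilatory support, after extubation;
- new voice change;
- an open item for any other adverse event.

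Record them at the existing 15, 30 and 60 min and 6, 12 and 24 h assessments, and state a definition and an assessor for each. Keep nerve injury and haematoma for both arms. Record Horner signs, local anaesthetic toxicity and intravascular injection as block-related items reported for Group A. Add the whole set to Measurement tools, so that the outcome has a matching data source.

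Report counts by arm with exact confidence intervals, and state in the analysis section that they are descriptive because 33 per arm gives little power. This changes recording only, not treatment.

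The cost is a few more items on the record form at assessments already scheduled. The drawback is that voice change has surgical causes in both arms and would be scored without any described blinding, so a between-arm difference must be read cautiously.
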